8.2 Sample Size Calculation

In order to justify continuing to explore pembrolizumab in combination with chemoradiation in a larger study, we must establish that the true underlying risk of unacceptable toxicities (UT's) in the population is acceptably low. To this end we need to decide upon values for a number of important parameters. Firstly, we need to decide upon a decision threshold for the maximum number of UT's allowable in the study sample before we conclude that the regimen is unsafe. In the event that the regimen is concluded to be unsafe, it should either be modified upon recommendation of the TMC before being considered further, or abandoned.

Additionally, we need to define two limits on the true underlying UT rate. The first is a “definitely considered safe” limit, defined such that if the true underlying UT rate is at this limit (or below) then we want to be confident that our decision threshold on the sample will yield a high probability that we will continue into a larger study focused on efficacy. The second is a “definitely considered unsafe” limit, defined such that if the true underlying UT rate is at this limit (or above) then we want to be very confident that our decision threshold on the sample will yield a high probability that we will discontinue – i.e. that we will reject the regimen as it currently stands for further consideration, and defer to the TMC for direction on whether and how to modify it.

To further mitigate risk, we would like accrual to proceed in two stages, with an interim analysis after the first stage at which stopping will be considered if the early evidence of a too high rate of UT's is convincing.

Under the proposed design, we desire to constrain the probability of discontinuation if the true underlying UT rate is at the definitely considered safe limit to a maximum of 20%, and at the same time limit the risk of continuing if the true underlying UT rate is at the definitely considered unsafe limit to 10%. We would like to consider the “definitely considered safe” rate of UT's to be 30%, and the “definitely considered unsafe” rate of UT's to be 50%.

These goals can be achieved with a sample size of 30 patients. Consider a Simon's two stage design whereby accrual will be halted if we see greater than 5 UT's amongst the first 10 patients and greater than 11 amongst the first 30 patients. Given these stopping thresholds, if the true underlying UT rate is 0.3 then the cumulative probability of concluding unsafe after stage 2 of accrual will be 17% and if the true underlying rate of UT is 0.5 then the cumulative probability of concluding unsafe after stage 2 of accrual will be 90%. The relationship between the true underlying UT rate and the probability of concluding unsafe is shown in Figure 2.

[figure not shown]

Figure 2: Probability of concluding unsafe as a function of true underlying UT rate

As a secondary objective, we desire to test for an initial signal of efficacy by estimating the proportion of patients achieving a best response of complete response (CR). (See sections 3.2 and 7.1.2.6.2 for the definition of best response.) Similar to the procedure for placing thresholds on the number of UT's we define a threshold for the minimum number of CR's that must be seen in the sample in order to consider the regimen worthy of further investigation on the basis of efficacy. We also define a "maximum uninteresting" true underlying CR rate – the true underlying CR rate at or below which we would not consider the regimen clinically worthy of implementation, and a "minimum interesting" true underlying CR rate – the true underlying CR rate at or above which we would consider the regimen clinically worthy of implementation. We define the maximum uninteresting and the minimum uninteresting rates as being 0.5 and 0.7 respectively. If we place the decision threshold at 18 CR's out of 30, then the probability of judging the regimen worthy of further investigation for efficacy if the true underlying CR rate is 0.5 is 10%, and the probability of judging the regimen worthy of further investigation for efficacy if the true underlying CR rate is 0.7 is 84%. This is illustrated in Figure 3.

[figure not shown]

Figure 3: Probability of further investigation as a function of true underlying CR rate.

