3.2 Secondary Objectives, Hypothesis & Endpoint

Objectives:

- (1) To evaluate the efficacy of the addition of pembrolizumab to concurrent chemoradiation regimen by estimating the complete response rate (see below).
- (2) To characterize:
 - a. overall survival (OS);
 - b. metastatic disease-free survival (MDFS); and
 - c. locoregional progression free survival (LRPFS).

Hypothesis: The addition of pembrolizumab will improve the efficacy of chemoradiation in patients with bladder cancer.

Endpoints:

- (1) Best response, defined as the better of the responses achieved at either the 1st or 2nd cystoscopic examination after completing therapy. (The 1st and 2nd cystoscopic

examinations take place during weeks 19 and 31 respectively of the trial.) See section 7.1.2.6.2 for definitions of the response levels.

(2) Dates of

- i) death,
- ii) detection of metastatic disease,
- iii) detection of locoregional progression,
- iv) any initiation of any new non-protocol anti-cancer therapy

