4.2 Rationale for the combination of pembrolizumab with chemotherapy and radiation

Chemoradiotherapy leads to outcomes similar to cystectomy. However, a significant proportion of patients still fail to achieve a complete response to chemoradiation, require a cystectomy, relapse locally, or develop distant metastatic disease.

Approximately 30% of patients fail to achieve a complete response to therapy, with a relapse rate of 10% with local-regional disease, and 9-20% distant metastatic disease over 2 years [1, 2, 7, 12]. Improvements in these outcomes are desired.

The use of drugs such as pembrolizumab is transforming cancer medicine, and checkpoint inhibitors are resulting in unprecedented disease response rates and longer-term control. However, while a subgroup of bladder cancer demonstrate exquisite responses to these agents, many patients do not derive any benefit. A major challenge therefore is to develop rational strategies by which the activity of these agents can be broadened.

One potential approach is the combination of immunotherapy with radiation therapy. Radiation therapy induced cell killing has the potential to stimulate the release of tumour antigens and trigger antigenic stimulation. Proof of this concept is provided by *in vitro* studies [13], and anecdotally from clinical observations of tumour regressions at unirradiated tumour sites (the abscopal effect). Importantly, the combination of radiotherapy with immune check point inhibitors has been reported to escalate antitumour responses in clinical case reports [14], and shown to be safe when combined with radiation in several trials [15]. The effect of this combination in bladder cancer however has not been extensively investigated.

Predicting the impact of combining chemotherapy with immunotherapy is less straightforward. While chemotherapy may deplete immune effector cells, the cytotoxic effects of chemotherapy may also enhance antigen-release and stimulate immune responses as postulated for radiation therapy. In preclinical mouse models, chemotherapy synergises with anti-PDL1 treatment to

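### The complete-response rule in 8.2 cannot signal added efficacy at the protocol's own chemoradiotherapy rates, and its threshold of 18 does not give the stated 10% and 84%

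*Combined protocol and SAP*

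**What the plan says.** Section 3.2 hypothesises: "The addition of pembrolizumab will improve the efficacy of chemoradiation in patients with bladder cancer". The endpoint is best response, the better of two cystoscopies: "examinations take place during weeks 19 and 31 respectively of the trial".

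Section 8.2 turns this into a decision rule. It says "we desire to test for an initial signal of efficacy", then "we define a threshold for the minimum number of" CRs that would make the regimen worth pursuing for efficacy. The reference rates follow: "We define the maximum uninteresting and the minimum uninteresting rates as being 0.5 and 0.7 respectively". The sentence before defines the upper rate as the minimum interesting one, so the repeated label is a slip. The cut-off is given as "If we place the decision threshold at 18" CRs of 30, with a stated pass probability of 10% at a true CR rate of 0.5 and 84% at 0.7. Figure 3 is captioned "Probability of further investigation as a function of true underlying CR rate".

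The background sections give CR rates for chemoradiotherapy. Section 4.2 states: "Approximately 30% of patients fail to achieve a complete response to therapy", which is a CR rate of about 70%. Section 4.2.4.1 puts contemporary series at roughly 70-85%, and splits pathological CR by resection: 73-79% after a visually complete TURBT and 50-63% after an incomplete one. Section 5.1.2 requires maximal safe resection, which is not the same as visually complete.

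Section 8.3 plans Clopper-Pearson 95% intervals. Section 8.5 places the secondary efficacy analyses, CR included, at 3 years after the last registration.

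**The concern.** Two things look wrong in the rule itself.

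First, the rate called interesting, 0.7, is the protocol's own figure for existing chemoradiotherapy and the bottom of its contemporary range. Section 8.2 gives no source for 0.5 or 0.7 and does not set them against those figures. If chemoradiotherapy alone already gives 70% or more in these patients, passing is the expected result with no contribution from pembrolizumab. A reader who takes the words about an efficacy signal together with the hypothesis in 3.2 could report a pass as evidence of improvement.

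Second, the text makes 18 the smallest passing count, but the printed probabilities belong to a different cut-off. If exactly 18 CRs occur, the wording says go on and the error rates say do not. Settling that after the count is known would look data-driven.

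A lesser point is timing. Best response is known at week 31, yet the CR analysis waits for the survival follow-up.

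**Working it through.** **Inputs.** n = 30; reference rates 0.5 and 0.7; threshold 18; stated pass probabilities 10% and 84% (all 8.2). Cited CR rates: about 0.70 (4.2); 0.70-0.85 overall, 0.73-0.79 after visually complete and 0.50-0.63 after incomplete TURBT (4.2.4.1).

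**Formula.** With X the number of CRs and p the true CR rate, P(X ≥ r) = Σ C(30,k) p^k (1−p)^(30−k), summed over k = r to 30.

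**1. Reproducing the stated 10% and 84%**

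| Passing rule | p = 0.5 | p = 0.7 |
|---|---|---|
| X ≥ 18 (18 as the minimum) | 0.1808 | 0.9155 |
| X ≥ 19 (more than 18) | 0.1002 | 0.8407 |
| Stated in 8.2 | 10% | 84% |

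At p = 0.5 and r = 19 the sum is 107,636,402 / 2^30 = 0.1002. Adding C(30,18) / 2^30 = 86,493,225 / 1,073,741,824 = 0.0806 gives 0.1808 for r = 18. The printed figures fit only X ≥ 19.

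The two readings part only at X = 18. The chance of that count is 8.1%, 14.7% and 7.5% at p = 0.50, 0.60 and 0.70.

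**2. Pass probability if pembrolizumab adds nothing** (X ≥ 19, the stricter reading)

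| True CR rate | P(pass) |
|---|---|
| 0.50 | 10% |
| 0.60 | 43% |
| 0.63 | 57% |
| 0.65 | 65% |
| 0.70 | 84% |
| 0.73 | 92% |
| 0.75 | 95% |
| 0.79 | 99% |
| 0.80 | 99% |
| 0.85 | 99.9% |

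Over 70-85% the rule passes 84% to 99.9% of the time. By resection stratum it passes 92-99% of the time at 73-79% (visually complete) and 10-57% at 50-63% (incomplete).

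**3. What a pass at the boundary shows.** At 19/30 the one-sided 90% lower limit is 0.4999, in line with a one-sided level of 0.1002. The planned two-sided 95% intervals are:

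- 19/30: 0.439 to 0.801
- 20/30: 0.472 to 0.827
- 21/30: 0.506 to 0.853

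So 19 or 20 CRs pass the rule while the reported interval still includes 0.50. The chance of 19 or 20 CRs is 7.9%, 25%, 30% and 25% at p = 0.50, 0.60, 0.65 and 0.70.

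**4. Timing.** Three years is 156.5 weeks; 156.5 − 31 = 125.5 weeks, about 2.4 years. This ignores the gap of up to 10 days between registration and first treatment.

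**The case against.** The strongest reply is that 8.2 never presents the rule as a comparison with chemoradiotherapy. It defines 0.5 and 0.7 by clinical worth, the trial is a single-arm pilot without a control, and 8.2 bases the move to a larger trial on unacceptable toxicity. A floor on CR is a legitimate secondary screen in such a design.

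The 84-99.9% range also depends on which benchmark is used. The table in 4.1.2 includes chemoradiotherapy series with CR rates of 50, 55, 61, 63 and 66%, at which X ≥ 19 has probability 10, 23, 48, 57 and 70%. Some of those series gave neoadjuvant chemotherapy and assessed response after about 40 Gy, so no single benchmark carries over cleanly. The trial also takes the better of two cystoscopies and requires no metastatic disease; whether the cited series did the same cannot be checked from these documents.

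Much of this stands as a limit on emphasis. The no-benefit rate is not settled, and a floor is acceptable. But the protocol does not make that argument: nothing ties 0.5 to the lower rates, while 3.2 and the efficacy-signal wording invite the stronger reading. Figure 3 plots pass probability against the true rate, but the text does not place the cited rates beside it.

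On the threshold, the calculation is right for more than 18, the same form as the toxicity rule in 8.2. The error is in the wording, but the wording is what will be applied. The overlap between the rule and the 95% interval is simply what a one-sided 10% rule produces, and Table 10 already brackets it with 18/30 and 21/30. It needs explaining; it is not a defect.

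**Conclusion.** The concern holds. The threshold error is definite: as written the rule has error rates of 18% and 92% in place of 10% and 84%, and the readings conflict at exactly 18 CRs.

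The benchmark point holds given the protocol's own figures. If chemoradiotherapy alone yields 70-85% CR in these patients, a pass is 84-99.9% likely with no added benefit. If the population resembles the incompletely resected group at 50-63%, the figure is 10-57%. Either way, a pass rejects a true CR rate of 0.50 or lower only at a one-sided level of about 10%, and is not evidence for the hypothesis in 3.2. These figures assume 30 evaluable patients, independent outcomes and the X ≥ 19 reading; X ≥ 18 is more lenient.

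The timing point is minor. Progression to a larger trial rests on toxicity, so late CR results do not undermine that decision; they arrive about 2.4 years later than they could. Because CR is a secondary endpoint, this should be corrected but does not threaten the primary objective.

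**What to change.** 1. **Section 8.2, before CR counts are reviewed.** State the rule as at least 19 CRs of 30 (more than 18), and correct the second rate's label to minimum interesting. Add: *Meeting the threshold rejects a true CR rate of 0.50 or lower only at a one-sided level of about 10% (exact 0.1002); it is not evidence that pembrolizumab improves CR over chemoradiotherapy.* Beside Figure 3, tabulate the pass probabilities at 0.60 to 0.85 against the rates cited in 4.2 and 4.2.4.1.
2. **Section 3.2.** Add: *This single-arm trial does not test this hypothesis against chemoradiotherapy alone.*
3. **Section 8.5.** Move the CR analysis to the second analysis, when the last patient reaches week 31. Leave OS, DMFS and LRPFS at 3 years.
4. **Optional.** Report week-19 CR with its Clopper-Pearson interval beside best response, as description only. Note that the protocol times the cited assessments differently: 6-12 weeks after starting chemoradiotherapy in 4.2.4.1, and 12 weeks after completing it in 4.1.2.

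This keeps the plan's stated error rates and makes the threshold no stricter than they imply.

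**Cost.** One protocol amendment with HREC approval (12.2), because the SAP is section 8 of the protocol; one small table; and one earlier analysis of data already collected. No patients or visits are added. The downsides are a more modest efficacy claim and CR results known while follow-up continues, in a trial that is already open-label (10.3).

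### The complete-response threshold of 18 out of 30 does not give the stated 10% and 84%: read as the minimum count the plan says it is, it gives 18% and 92%

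*Combined protocol and SAP*

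**What the plan says.** Section 8.2 (Sample Size Calculation) sets a decision rule for the secondary efficacy objective, the proportion of patients whose best response is a complete response.

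- Meaning of the threshold: "we define a threshold for the minimum number of CR's that must be seen in the sample". Meeting it is the condition for pursuing the regimen on efficacy grounds.
- Its value: "If we place the decision threshold at 18 CR's out of 30".
- The two reference rates: "We define the maximum uninteresting and the minimum uninteresting rates as being 0.5 and 0.7 respectively". The second label is a slip, because the sentence before it defines that rate as the minimum interesting one.
- The stated operating characteristics: "the probability of judging the regimen worthy of further investigation for efficacy if the true underlying CR rate is 0.5 is 10" per cent, and "the probability of judging the regimen worthy of further investigation for efficacy if the true underlying CR rate is 0.7 is 84" per cent.

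For unacceptable toxicity (UT), the same section treats the threshold as the largest count still tolerated. It stops when that count is exceeded: more than 5 UTs in the first 10 patients, or more than 11 in 30.

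**The concern.** A minimum that has to be seen is satisfied when it is reached, so a threshold of 18 means going on at 18 or more CRs. The stated probabilities look too low for that rule at both reference rates, which suggests that they were calculated for a rule one count stricter.

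This is the only efficacy decision rule in the plan. If the wording governs, the risk of a false positive decision is understated. If the probabilities govern, the count in the text is wrong by one. The trial is single-arm and open-label, so a boundary left open would be settled by people who already know the count, which is what a prespecified threshold is meant to prevent.

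**Working it through.** **Inputs, all from section 8.2:** n = 30; threshold 18; true CR rates 0.5 and 0.7; stated probabilities of going on 10% and 84%.

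**Formula.** With X the number of CRs among 30 patients and p the true rate, the chance of going on under the rule X ≥ r is

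P(X ≥ r) = Σ (x = r to 30) C(30, x) pˣ (1 − p)³⁰⁻ˣ.

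**Step 1: try to reproduce the stated figures.**

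| Rule | p = 0.5 | p = 0.7 |
|---|---|---|
| X ≥ 17 | 29.2% | 96.0% |
| X ≥ 18 (the rule as worded) | 18.1% | 91.6% |
| X ≥ 19 (more than 18) | 10.0% | 84.1% |
| X ≥ 20 | 4.9% | 73.0% |
| Stated in the plan | 10% | 84% |

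The stated pair agrees with X ≥ 19 on both figures and with X ≥ 18 on neither.

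**Step 2: could an approximation explain the gap?** A normal approximation for X ≥ 18 gives 13.7% and 88.4% without continuity correction, and 18.1% and 91.8% with it. Neither pair matches, so the difference lies in the rule and not in the method.

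**Step 3: how often would it matter?** The two readings differ only at X = 18, and the probability of that count is the difference between the two tails.

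- p = 0.5: 0.1808 − 0.1002 = 0.0806 (8.1%)
- p = 0.6: 0.5785 − 0.4311 = 0.1474 (14.7%)
- p = 0.7: 0.9155 − 0.8407 = 0.0749 (7.5%; the last digit comes from unrounded values)

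**Step 4: is the UT rule affected in the same way?** Let X₁ be the UT count in the first 10 patients and X₂ the count in the next 20. The probability of concluding unsafe is

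P(X₁ ≥ 6) + Σ (x = 0 to 5) P(X₁ = x) · P(X₂ ≥ 12 − x).

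This gives 17.7% at a true UT rate of 0.3 and 90.5% at 0.5, close to the stated 17% and 90%. There the strict inequality in the text and the calculation agree. The mismatch is confined to the CR rule.

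**The case against.** The best defence is that the authors meant more than 18. The CR rule is introduced as analogous to the UT rule, where the quoted number has to be exceeded. On that convention both stated probabilities come out correctly to rounding, so the calculation is probably sound and the word for minimum was used loosely. This is a likely account of how the mismatch arose.

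It does not remove the mismatch. The analogy fails on the point at issue: the UT number is a tolerated maximum, so exceeding it is the natural trigger, whereas the CR number is a required minimum, so reaching it is. Nowhere does the plan say more than 18, or at least 19, for CR. Figure 3 was not available for this check. It may show which rule was calculated, but it would not change the sentence in the text.

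The points about scale do stand:

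- CR is a secondary objective, and the 20% and 10% error limits in section 8.2 apply to UT only. For CR, no target is set that the literal rule would breach.
- The 30 patients are justified by the UT design.
- The CR threshold triggers no interim stopping. Under section 8.5, efficacy is analysed once, after the last patient is three years past registration.
- The CR proportion will be reported with a Clopper-Pearson interval whichever reading applies; Table 10 gives 0.41 to 0.77 for 18 of 30.
- The two readings lead to the same decision at every count except 18.

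**Conclusion.** The concern holds. Read literally, the rule carries an 18.1% chance of going on at a true CR rate of 0.5, against 10% stated, which is a ratio of about 1.8 (18.08/10.02). It has 91.6% power at 0.7, against 84% stated. The stated figures are correct for a threshold of 19.

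The result assumes that all 30 patients count in the denominator and that their responses are independent with a common rate, which is the model the plan's own figures imply. The size of the understatement depends on taking the threshold as a minimum count. If more than 18 was intended, the probabilities stand and the wording is the error. Either way, the text and its error rates cannot both be right, and they conflict on the action at exactly 18 CRs. This should be settled before CR data are analysed.

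**What to change.** Restate the rule in section 8.2 in one of two ways:

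1. Go on if at least 19 of 30 patients (more than 18) have a complete response, keeping 10% and 84%.
2. Go on if at least 18 of 30 have a complete response, and give the probabilities as 18% and 92%.

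The first preserves the published operating characteristics and is probably what was calculated. The second keeps the number in the text but accepts a less favourable false-go risk. Check Figure 3 against the chosen rule and redraw it if it shows the other one. In the same edit, relabel 0.7 as the minimum interesting rate.

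The cost is one sentence of SAP text and possibly one figure. No patients, visits or procedures change.

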8.3 Methods of analysis

Binary proportions (UT and CR proportions) and their 95% CI's will be provided using the Clopper-Pearson method. Table 10 provides estimates and 95% CI's for various observed counts from a sample size of 30.

Table 10: Estimated proportions and corresponding 95% CI's for a sample size of 30.

Count	Estimate	95% CI
3	0.1	[0.02, 0.27]
6	0.2	[0.08, 0.39]
9	0.3	[0.15, 0.49]
12	0.4	[0.23, 0.59]
15	0.5	[0.31, 0.69]
18	0.6	[0.41, 0.77]
21	0.7	[0.51, 0.85]
24	0.8	[0.61, 0.92]
27	0.9	[0.73, 0.98]

When estimating the UT rate and its 95% CI, the methods of Jung & Kim (2004) and Koyama & Chen (2008) will be used to adjust for the two stage sampling procedure.

It is expected that it will take two years to accrue the required 30 patients. Accrual will not be suspended pending the results of the interim analysis.

OS, DMFS and LRPFS will be characterized using Kaplan-Meier curves.

Both DMFS and LRPFS will be measured from the date of patient registration. DMFS will be measured until the date of first commencement of any non-protocol anti-cancer therapy, detection of distant metastasis, or death due to any cause. LRPFS will be measured until the date of first commencement of any non-protocol anti-cancer therapy, detection of local or regional progression, or death due to any cause. Occurrence of distant metastasis will be a censoring event for measurement of LRPFS. There are no censoring events for DMFS.

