8.5 Timing of Analyses

A total of three analyses will be performed.

1. The interim analysis for the primary objective (feasibility) will take place after the 10th patient has reached the 31 week assessment time point.
2. Provided that the interim analysis does not result in the trial being closed prematurely due to unacceptable toxicity, the final analysis for the primary objective will take place after the last patient has reached the 31 week assessment time point.
3. Provided that the interim analysis does not result in the trial being closed prematurely due to unacceptable toxicity, the analysis for the secondary efficacy objectives, as well as the analysis of any exploratory objectives, will take place after the last patient has reached 3 years past registration.

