9.0 SAFETY PARAMETERS/REVIEW AND MODIFICATIONS TO TRIAL

Given the experimental nature of the addition of pembrolizumab to concurrent chemoradiation, the following safety measures will exist

- 1) The trial operations executive (TOE) and the trial management committee (TMC) will review safety issues related to the trial through regular teleconferences held throughout the trial.
- 2) An additional safety review by the TMC will take place 12 weeks after completion of treatment for the 10th patient whereby accrual will be halted if we see greater than 5 UT's amongst the first 10 patients recruited using the Simon's two stage design described above in 8.2. Accrual can continue until the results of the interim analysis are available to the TMC.
- 3) Modifications to trial
 - a. Based on safety discussion the TMC may recommend to either
 - i. Omit concurrent pembrolizumab with chemoradiotherapy, and give pembrolizumab 200mg IV q3 weekly at week 7, 10, 13, 16 and 19 alone
 - ii. Modify the chemotherapy arm to allow either carboplatin, or 5FU/MMC [8]
 - iii. Suspend the study

iv. Any other modification suggested to reduce toxicity made by the TMC

The enrolment to the trial will be monitored by the TMC and if enrolment is reduced due to concerns regarding design of the trial, the TMC will suggest modifications that may include modification of the chemotherapy arm to allow concurrent carboplatin or 5FU/MMC.

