11.0 STUDY COMMITTEES

11.1 Trial Management Committee

This study is conducted by the Australian and New Zealand Urogenital and Prostate Cancer Trials Group (ANZUP) in collaboration with the Centre for Biostatistics and Clinical Trials (BaCT) who will coordinate this study

Study coordination, data acquisition and management and statistical analysis will be performed by the Centre for Biostatistics and Clinical Trials at Peter Mac.

The Trial Management Committee (TMC) will oversee study planning, monitoring, progress, review of information from related research, and implementation of recommendations from other study committees and external bodies (e.g. ethics committees).

The TMC will consider whether to continue the study as planned, modify, or stop it, based on reports provided by the BaCT or other information.

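### Worth considering: halt accrual when the 6th unacceptable toxicity among the first 10 patients is confirmed, instead of waiting for patient 10's week 31. The error rates do not change.

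*Combined protocol and SAP*

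**What the plan says.** Section 8.2 adopts two stages to limit risk, "with an interim analysis after the first stage at which stopping will be considered", and states the rule without a date: "whereby accrual will be halted if we see greater than 5" UTs in the first 10 patients. The final limit is more than 11 of 30.

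The date comes elsewhere. Section 8.5 says the interim analysis "will take place after the 10th patient has reached the 31 week assessment time point". Section 9.0 places the review 12 weeks after patient 10 completes treatment, which is also week 31 if treatment runs to week 19.

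Accrual stays open meanwhile. Section 8.3 says "Accrual will not be suspended pending the results of the interim analysis", and Section 9.0 says "Accrual can continue until the results of the interim analysis are available to the TMC".

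Other oversight exists. Under Section 9.0 the trial operations executive and the TMC "will review safety issues related to the trial through regular teleconferences held throughout the trial", and "Based on safety discussion the TMC may recommend to either" one of several changes, including suspension. Section 11.1 adds "The TMC will consider whether to continue the study as planned, modify, or stop it". None of these passages gives a UT count at which the committee must act before the interim analysis.

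**The concern.** A UT is the occurrence of any one listed event, so once confirmed it stays confirmed. Full follow-up to week 31 is needed to declare stage 1 passed. It is not needed to declare it failed: after 6 UTs among the first 10, no later data can bring the count back to 5.

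Followed as dated, the plan lets patients be enrolled after its own stage-1 limit has been crossed, unless the TMC chooses to act. This matters only in trials that cross. At a true UT rate of 0.5, the rate Section 8.2 treats as definitely unsafe, that is more than a third of trials.

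**Working it through.** **Inputs from the documents.** Limits of more than 5 in 10 and more than 11 in 30, UT rates of 0.3 and 0.5, and stated probabilities of concluding unsafe of 17% and 90% (8.2). Thirty patients in two years (8.3). Look at patient 10's week 31 (8.5).

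**Assumptions.** Even accrual. UT onset times are not given, so they were varied from all within weeks 0–7 to all at week 31. Confirmation lag is 0 or 6 weeks, applied to both the trigger and the planned look.

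**1. The plan's own figures.** P(unsafe) = P(X₁₀ ≥ 6) + Σ over x = 0 to 5 of P(X₁₀ = x) · P(X₂₀ ≥ 12 − x).

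| True UT rate | P(cross at stage 1) | P(unsafe) | Stated |
|---|---|---|---|
| 0.3 | 0.047 | 0.1769 | 17% |
| 0.5 | 0.377 | 0.9048 | 90% |

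The stated figures reproduce to within a percentage point and meet the plan's targets (at most 20% wrongly discontinuing, at most 10% wrongly continuing).

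**2. When the look falls.** Pace = 30 / (24 × 30.44 / 7) = 0.2875 patients per week. Look = 10 / 0.2875 + 31 = 65.8 weeks. Enrolled by then = 65.8 × 0.2875 = 18.9, that is 18 whole patients.

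**3. Effect of the trigger on error rates.** A 6th UT among the first 10 is the same event as crossing the stage-1 limit. Exactly the same trials stop, so the table in step 1 is unchanged.

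**4. Enrolment at a stage-1 stop.** UT rate 0.5, simulated (400,000 trials per setting). Expected N = 30 − 0.377 × (30 − enrolled at the stop), provided a crossing ends accrual. As planned: 30 − 0.377 × (30 − 18) = 25.48. Expected N in the table uses unrounded enrolment.

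| UT onset (weeks) | Enrolled at stop (plan 18) | Median lead over look (weeks) | Expected N (plan 25.48) | Saving | Stops with fewer than 10 enrolled |
|---|---|---|---|---|---|
| 0–7 | 9.2 | 31.3 | 22.18 | 3.30 | 52.7% |
| 1–20 | 11.5 | 24.1 | 23.03 | 2.45 | 13.0% |
| 1–31 | 13.5 | 17.1 | 23.80 | 1.68 | 2.7% |
| 19–31 | 15.5 | 10.0 | 24.52 | 0.95 | 0% |
| all at 31 | 16.7 | 3.5 | 25.00 | 0.48 | 0% |

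The first row is an optimistic bound. Radiation running past 7 weeks cannot be confirmed by then. Nor can a delay of more than 6 weeks in the pembrolizumab dose due in week 4, which is known only after week 10.

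**5. Sensitivity.**
- Six-week lag: 11.0 to 18.7 enrolled, against 20 as planned. Stops with fewer than 10 enrolled: 0 to 14.5%.
- UT rate 0.3: expected N 29.04 to 29.39, against 29.43, a saving of 0.04 to 0.4.
- UT rate 0.6: expected N 16.7 to 21.4, against 22.4.
- Half the planned pace (UT rate 0.5): 8.7 to 12.7 enrolled, against 14.
- With all onsets in weeks 0–7 and no lag, the share of stops before 10 are enrolled rises to about 67% at half pace and about 63% at a UT rate of 0.6.

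**6. Which patients count.** Only UTs in the first 10 may feed the trigger. If the 6th UT in any enrolled patient before the look triggered the halt, P(unsafe) at 0.3 would rise to about 28–47% (onset over weeks 0–31 down to 0–7).

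**The case against.** Keeping accrual open is a deliberate choice, stated in both 8.3 and 9.0, and two-stage designs commonly look only when stage 1 is fully assessed. Section 8.2 gives the rule without a date, so it can be read as already covering an early crossing. Section 9.0 makes the week-31 review additional to regular teleconferences, toxicity is assessed at every visit, and the TMC may suspend, modify or stop the study. Six UTs in ten patients would probably be noticed. Section 8.2 also says only that stopping will be considered. If the TMC modifies the regimen and continues, the expected-N savings do not apply.

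Most of this stands, and it is why the point is a refinement. What remains is that the dated passages do not confirm the early reading, and discretion carries no count that obliges action.

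A reader might infer that patients are unprotected until week 31, that the plan forbids an earlier stop, or that its operating characteristics are wrong. The documents support none of these: the committee has the power to act at any time, and the 17% and 90% reproduce. Nor does the point require accrual to be suspended while the interim analysis is awaited. With fewer than 6 UTs, open accrual is a legitimate choice.

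**Conclusion.** The point holds as an inexpensive improvement to consider. The direction is certain, because the 6th UT can never be confirmed later than the planned look. The decision probabilities are unchanged, and no trial that would pass stage 1 is cut short.

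The size is modest and rests on assumed onset times and even accrual. It arises only in trials that cross, and the expected-N figures hold only if a crossing ends accrual. With onset spread over weeks 1–31, the saving at a UT rate of 0.5 averages 1.7 patients over all trials. Among trials that stop at stage 1, it is about 4.5 fewer enrolled (18 − 13.5).

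**What to change.** **First, reconcile the UT wording**, so that a confirmed UT has one meaning. Which rule is right is for the sponsor.
- Cisplatin omission: 4.2.4.1 allows up to two omitted doses, while 3.1 and 8.1 count two or more withheld doses as a UT.
- Cisplatin reduction: 4.2.4.1 requires no dose reduction, while 3.1 and 8.1 use less than 66% of the intended total.
- Toxicity window: 12 weeks from scheduled completion (3.1, 4.2.4.1) or from completion (8.1). These can differ for patients who stop early.

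**Then add to 8.2, 8.5 and 9.0:**

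> UTs among the first 10 patients recruited (the same set used at the interim analysis) are tallied as the trial centre confirms them under the UT definition in 8.1. When the 6th is confirmed, accrual is halted and the TMC convened without waiting for week 31. UTs in later patients do not count toward this limit. With fewer than 6, stage 1 is passed only at the week-31 look. Patients already enrolled are followed to week 31 for UT assessment.

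Accrual otherwise stays open and the limit of more than 11 of 30 is unchanged. The change concerns accrual only, not the treatment of patients already enrolled.

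**Add to 8.3.** If 10 or more are enrolled at the halt, take the stage-1 count at week 31 and apply the planned two-stage adjustment. If fewer than 10, report the UT count and proportion with week-31 follow-up of everyone enrolled, state that sampling was curtailed, and use a pre-specified estimator and confidence interval for curtailed (inverse-binomial type) sampling.

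**Cost.** Wording in four sections plus the UT reconciliation, a running tally for 10 patients, and the chance of a halt before 10 are enrolled. At a UT rate of 0.5 and planned pace that is 0 to 53% of stage-1 stops with no lag, and 0 to 14.5% with a 6-week lag. It is higher in the slow-accrual and high-rate cases in the working.
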